#### Time at risk (days)

Total time at risk attributed to each dose will be obtained by summing the time(s) at risk at each specific dose in each individual study period and deducting n-1, where n is the number of non-consecutive periods covered that are being summed. Total time at risk attributed to BKZ Total will be obtained by using the time at risk algorithms specified for subjects who do not switch study treatments in Section 10.1.5.1.

- Time at risk at each specific dose in each individual study period is calculated separately as follows:

- Attributed to BKZ 320mg Q4W:

- Date of first BKZ 320mg Q8W dose in the next study period – date of first BKZ 320mg Q4W dose in the current study period.

Note: If BKZ 320mg Q4W is the last dosing schedule received in the last study period, then this calculation reverts to:

- For all subjects, use the minimum of the following:
- Date of last BKZ 320mg Q4W dose in the current study period – date of first BKZ 320mg Q4W dose in the current study period + 140 days.
- Date of first BKZ 320mg Q8W dose in OLE2 - date of first BKZ 320mg Q4W dose in the Open-Label Extension Period + 1 day. The OLE and The OLE2 treatment periods should not overlap by more than 1 day
- Date of last clinical contact – date of first BKZ 320mg Q4W dose in the OLE Period + 1.
- Date of death – date of first BKZ 320mg Q4W dose in the current study period + 1

- Attributed to BKZ 320mg Q8W:

- Date of first BKZ 320mg Q4W dose in the next study period – date of first BKZ 320mg Q8W dose in the current study period.

Note: If BKZ 320mg Q8W is the last dosing schedule received in the last study period, then this calculation reverts to:

- For subjects who die

Date of death – date of first BKZ 320mg Q8W dose in the current study period + 1.

For all other subjects, use the minimum of the following:

- Date of last BKZ 320mg Q8W dose in the current study period – date of first BKZ 320mg Q8W dose in the current study period + 140 days.
- Date of first dose in OLE2 - date of first BKZ 320mg Q8W dose in the Open-Label Extension Period + 1 day.
- Date of last clinical contact – date of first BKZ 320mg Q8W dose in the OLE Period + 1.

### 10.1.6 Exposure during the OLE2 Period based on OLE2 set

Eligible subjects from sites in the US or Canada who have completed the Week 144 Visit or are in the SFU or have completed the SFU of the OLE Period can roll over to an additional OLE2 period.

Definitions for study medication duration (days) and time at risk (days) during the OLE2 Period will be provided for the following subjects:

- Group A: Subjects who roll over directly from OLE to OLE2
- Group B: Subjects who reinitiate bimekizumab and who were in the SFU or had completed the SFU of the OLE Period.

#### 10.1.6.1 Group A: Subjects who roll over directly from OLE to OLE2

Study medication duration (days)

- Date of last bimekizumab dose in the OLE2 Period – date of first dose in the OLE2 Period + 56 days

Note: If date of last bimekizumab dose in the OLE2 Period + 56 days extends to a date beyond the final visit date (including PEOT, but not including SFU2), then this calculation reverts to:

- Final visit date (including PEOT, but not including SFU2) – date of first dose in the OLE2 Period+ 1.

Note: For subjects who die, if date of last bimekizumab dose in the OLE2 Period + 56 days extends to a date beyond the date of death, then this calculation reverts to:

- Date of death – date of first dose in the OLE2 Period+ 1.

Time at risk (days)

- Use the minimum of the following:
  - Date of last dose in the OLE2 Period – date of first dose in the OLE2 Period + 140 days.
  - Date of last clinical contact – date of first dose in the Open-Label Extension Period + 1.
  - Date of death – date of first dose in the OLE2 Period+1.

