#### 10.1.4.1 For subjects who do not switch study treatments

Study medication duration (days)

- For subjects who receive Q4W in the Open-Label Extension Period (subjects who discontinue prior to switching to Q8W):
  - Date of last bimekizumab dose in the Open-Label Extension Period – date of first dose in the Open-Label Extension Period + 28 days (for subjects on Q4W dosing)
- For subjects who receive Q8W in the Open-Label Extension Period use the minimum of:
  - Date of last bimekizumab dose in the Open-Label Extension Period – date of first dose in the Open-Label Extension Period + 56 days
  - First dose date in Open-Label Extension 2 Period – date of first dose in the Open-Label Extension Period + 1

Note: If date of last bimekizumab dose in the Open-Label Extension Period + 28 days (or 56 days for subjects on Q8W dosing) extends to a date beyond the final visit date (including PEOT, but not including SFU), then this calculation reverts to:

- Final visit date (including PEOT, but not including SFU) – date of first dose in the Open-Label Extension Period + 1.

Note: For subjects who die, if date of last bimekizumab dose in the Open-Label Extension Period + 28 days (or 56 days for subjects on Q8W dosing) extends to a date beyond the date of death, then this calculation reverts to:

- Date of death – date of first dose in the Open-Label Extension Period + 1.

Time at risk (days)

- For all subjects, use the minimum of the following:
  - Date of last dose in the Open-Label Extension Period – date of first dose in the Open-Label Extension Period + 140 days,
  - Date of first dose in OLE2 - date of first dose in the Open-Label Extension Period + 1 day
  - Date of last clinical contact in OLE and SFU – date of first dose in the Open-Label Extension Period + 1.
  - Date of death – date of OLE first dose

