##### Time at risk (days)

- For all subjects, use the minimum of the following:
  - Date of last dose – date of first + 140 days.
  - Date of last clinical contact – date of first dose + 1.
  - Date of death – date of first dose + 1.

For subjects randomized to secukinumab at Baseline who initiate bimekizumab at Week 48 and continue on the same dose schedule in the OLE without switching, use the study medication duration and time at risk algorithms specified for subjects who do not switch study treatments in Section [10.1.4.1](#)

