#### 10.1.6.2 Group B: Subjects who reinitiate bimekizumab

##### 10.1.6.2.1 Subjects reinitiated to receive BKZ Q8W at OLE2 start

- Study medication duration (days)

- Date of last bimekizumab dose in the OLE2 period – date of first bimekizumab dose in the OLE2 + 56 days

Note: If date of last bimekizumab dose in the OLE2 + 56 days extends to a date beyond the final visit date (including PEOT, but not including SFU2), then this calculation reverts to:

- Final visit date (including PEOT, but not including SFU2) – date of first dose in the OLE2 Period + 1.

Note: For subjects who die, if date of last bimekizumab 320mg Q8W dose + 56 days extends to a date beyond the date of death, then this calculation reverts to:

- Date of death – date of first dose in the OLE2 Period + 1.

- Time at risk (days)

- Use the minimum of the following:

- Date of last dose – date of first dose in OLE2 + 140 days.
- Date of last clinical contact – date of first dose in OLE2 + 1. Date of death – date of first dose + 1.

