## Time at risk (days)

- Attributed to BKZ Q4W/Q8W:
  - Use the time at risk algorithm specified for subjects who do not switch study treatments in Section 10.1.6.1.

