- Listing of COVID-19 Vaccine Interval TEAEs

The following summaries will be provided for the BKZ Set by treatment at the time of AE onset. These tables will include AEs from both the double-blind and Open-Label treatment period (excluding OLE2 treatment period). AEs that occurred while subjects received secukinumab will not be included.

- Incidence of TEAEs Overview
- Incidence of TEAEs per 100 Subject-Years
- Incidence of Serious TEAEs per 100 Subject-Years
- Incidence of TEAEs by decreasing frequency of PT

- Incidence of TEAEs per 100 subject years by SOC, HLT, and PT and by Time of Onset Relative to COVID-19 pandemic (prior to COVID-19 pandemic, during COVID-19 pandemic).

In addition, all summaries of TEAEs based on “100 subject years” will include EAIR (with 95% CI) and EAER.

The following summaries will be presented for subjects who switched from secukinumab to bimekizumab at Week 48. The analyses will assign AEs according to the AE onset date relative to last secukinumab dose and accounting for approximately 5 times half-life (Onset  $\leq$  140 days from last secukinumab dose or Onset  $>$  140 days from last secukinumab dose):

- Incidence of TEAEs Overview
- Incidence of TEAEs per 100 Subject-Years
- Incidence of Serious TEAEs per 100 Subject-Years

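### Time at risk around OLE2 is misdefined in two places: the last-contact limit in 10.1.6.1 starts from the wrong dose and never applies, and the BKZ Total rule has no stop at OLE2 entry

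*SAP*

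**What the plan says.** **OLE2 time at risk.** For Group A, SAP 10.1.6.1 takes the minimum of three terms:

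- last dose: "Date of last dose in the OLE2 Period – date of first dose in the OLE2 Period + 140 days"
- last contact: "Date of last clinical contact – date of first dose in the Open-Label Extension Period + 1"
- death: "Date of death – date of first dose in the OLE2 Period+ 1"

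Group B subjects who restart on Q4W/Q8W are sent back to this rule by 10.1.6.2.2: "Use the time at risk algorithm specified for subjects who do not switch study treatments in Section 10.1.6.1". Group B subjects who restart on Q8W have their own rule in 10.1.6.2.1, where the last-contact term reads "Date of last clinical contact – date of first dose in OLE2 + 1".

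**BKZ Set time at risk.** For subjects who switch dose, 10.1.5.2 takes the BKZ Total value from 10.1.5.1. The minimum there has a last-dose term ("Date of last dose – date of first + 140 days"), a last-contact term and a death term. It has no term for entry into OLE2. The OLE rule in 10.1.4.1 does have one: "Date of first dose in OLE2 - date of first dose in the Open-Label Extension Period + 1 day". So do 10.1.4.2 (its Q8W part) and the dose-specific rules of 10.1.5.2.

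**Use.** Section 10.2.1 makes these definitions the basis of the exposure-adjusted AE summaries. Section 10.2.2 says of the BKZ Set summaries: "These tables will include AEs from both the double-blind and Open-Label treatment period (excluding OLE2 treatment period".

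**The concern.** In 10.1.6.1 the last-contact term exists to stop the clock when a subject is no longer observed. Counted from a dose given about 96 weeks too early, it stops nothing, and a subject lost during OLE2 keeps accruing time up to 140 days after the last dose. Two of the three OLE2 treatment columns then follow one rule and the third follows another.

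In the BKZ Total rule, numerator and denominator do not match. Time after the first OLE2 dose can enter the denominator, while events from that time are barred from the numerator. The Total column would also cover days that neither dose-specific column covers.

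Both slips push EAIR and EAER down, which makes bimekizumab look safer. They affect the OLE2 AE tables per 100 subject-years and the Total column of the pooled bimekizumab tables.

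**Working it through.** **Timeline check.** The stated maximum durations in 2.3.3 reproduce exactly. Group A: 5 (screening) + 144 + 40 (last OLE2 dose) + 20 (SFU2) = 209 weeks. No OLE2: 5 + 140 + 20 = 165. Group B after a full SFU: 5 + 136 + 20 + 4 + 40 + 20 = 225.

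**Inputs**, in nominal days with the first dose at day 0: first OLE dose 48 × 7 = 336; last OLE Q8W dose 136 × 7 = 952 (2.3.2); first OLE2 dose for Group A 144 × 7 = 1008; last OLE2 dose 184 × 7 = 1288 (Table 7–3). Last clinical contact is a maximum that includes the last dose date and any SFU2 visit (10.1), so it is never earlier than the last dose.

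**(a) Can the 10.1.6.1 last-contact term ever be the minimum?**

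Last-contact term minus last-dose term
= (contact − 336 + 1) − (last OLE2 dose − 1008 + 140)
= (contact − last OLE2 dose) + 672 + 1 − 140
≥ 533 days.

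If the visit windows in 3.1 (7 days at Week 48, 14 days at Week 144) are used in full, the gap is still at least 533 − 21 = 512 days. For Group B the interval between first OLE and first OLE2 dose is longer, so the gap is wider. The term never binds.

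Time at risk as written, and with the term counted from the first OLE2 dose:

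| OLE2 course | As written | Counted from first OLE2 dose | Excess |
|---|---|---|---|
| Last dose and last contact at OLE2 Baseline | 0 + 140 = 140 | 0 + 1 = 1 | 139 |
| Last dose Week 8, last seen Week 12 | 56 + 140 = 196 | 84 + 1 = 85 | 111 |
| Last dose and last contact at Week 24 | 168 + 140 = 308 | 168 + 1 = 169 | 139 |
| Last dose Week 40, last seen Week 48 | 280 + 140 = 420 | 336 + 1 = 337 | 83 |
| Last dose Week 40, SFU2 completed at Week 60 | 420 | min(420, 421) = 420 | 0 |

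**(b) BKZ Total for a bimekizumab-randomized Group A subject**, with last dose read as the last OLE dose:

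- as written: 952 + 140 = 1092 days
- stopped at OLE2 entry: 1008 + 1 = 1009 days
- excess: 83 days; 83 / 1009 = 8.2%

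The last-contact term does not prevent this, because it runs on through OLE2 to SFU2. It reduces the excess only for a subject lost within the first 12 weeks of OLE2, since day 1092 corresponds to Week 156.

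For a bimekizumab-randomized Group B subject who leaves the SFU early, a full 4-week OLE2 screening after Week 144 puts the first OLE2 dose at Week 148 at the earliest. The excess is then at most 1092 − (148 × 7 + 1) = 1092 − 1037 = 55 days. A Group B subject who completed the SFU (Week 136 + 20 = Week 156) has none.

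**The case against.** The intent is easy to recover. Section 10.1.6 is titled for the OLE2 Period, the other two terms of the 10.1.6.1 minimum use the first OLE2 dose, and 10.1.6.2.1 has the right origin. In 10.1.5.2 a remark under the Q4W rule says OLE and OLE2 should overlap by no more than a day. Section 10.1.5.1 itself was written for subjects who stay on Q4W throughout; after Protocol Amendment 5.0 such subjects would not normally reach OLE2, so the gap opens only through the BKZ Total cross-reference. All of this is fair. It shows what was meant, but a program written from the text would still produce the wrong denominators.

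The limits on scope also stand:

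- Part (a) changes only subjects whose last contact falls before last OLE2 dose + 140 days. SFU2 is planned for completers and withdrawals alike, and those who attend it on schedule are unaffected. Deaths have their own correctly anchored term, and Group B Q8W has the right rule.
- The 139-day cases are single-subject extremes: they need the last visit, last AE start, termination date and last dose all to fall on the dosing day.
- For EAIR, subjects with an event are counted only to first occurrence, so the excess comes from event-free subjects. EAER uses the full time at risk of everyone.
- Part (b) does not reach secukinumab-randomized subjects, whom 10.1.5.1 sends to 10.1.4.1, where the limit exists.

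A reader might also take last dose in 10.1.5.1 to mean the last dose in the whole study. BKZ Total would then be 1288 + 140 = 1428 days, 419 days or about 42% too long. The documents do not support that reading: 10.1.5 is confined by its heading to the double-blind and OLE periods, and 3.5.10 defines the BKZ Set by dosing in those periods.

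**Conclusion.** Both rules are wrong as written.

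(a) In 10.1.6.1, and through 10.1.6.2.2 for Group B Q4W/Q8W, the last-contact limit has no effect, and subjects lost before last OLE2 dose + 140 days are credited with up to 139 unobserved days each.

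(b) The BKZ Total rule admits OLE2 time without OLE2 events: about 83 days (8%) for a bimekizumab-randomized Group A subject who stays in contact through Week 156, and less for bimekizumab-randomized Group B subjects who enter OLE2 before finishing the SFU.

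These sizes assume nominal visit dates and the narrow reading of last dose. The direction is downward for EAIR and EAER. The aggregate bias cannot be computed, because the SAP gives neither the number of OLE2 subjects nor how many were lost early. It would be wrong to infer that all OLE2 participants are affected, or that pooled rates are off by 8% overall. The tables concerned are descriptive safety summaries, and OLE2 ran only in the US and Canada. This should be fixed, but it does not threaten the main conclusions.

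**What to change.** - In 10.1.6.1, count the last-contact term from the first dose in the OLE2 Period. Section 10.1.6.2.2 inherits the correction, and all three OLE2 columns then follow the same last-contact rule.
- In the BKZ Total rule (10.1.5.2 with 10.1.5.1), state that last dose means the last double-blind or OLE dose, and add one term to the minimum: date of first dose in OLE2 − date of first bimekizumab dose + 1.

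The cost is two wording changes and a re-run of the time-at-risk derivation and the exposure-adjusted tables that use it. No new data are needed.

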#### 10.1.6.2 Group B: Subjects who reinitiate bimekizumab

##### 10.1.6.2.1 Subjects reinitiated to receive BKZ Q8W at OLE2 start

- Study medication duration (days)

- Date of last bimekizumab dose in the OLE2 period – date of first bimekizumab dose in the OLE2 + 56 days

Note: If date of last bimekizumab dose in the OLE2 + 56 days extends to a date beyond the final visit date (including PEOT, but not including SFU2), then this calculation reverts to:

- Final visit date (including PEOT, but not including SFU2) – date of first dose in the OLE2 Period + 1.

Note: For subjects who die, if date of last bimekizumab 320mg Q8W dose + 56 days extends to a date beyond the date of death, then this calculation reverts to:

- Date of death – date of first dose in the OLE2 Period + 1.

- Time at risk (days)

- Use the minimum of the following:

- Date of last dose – date of first dose in OLE2 + 140 days.
- Date of last clinical contact – date of first dose in OLE2 + 1. Date of death – date of first dose + 1.

#### 10.1.6.2.2 Subjects reinitiated to receive BKZ Q4W/Q8W at OLE2 start

- Attributed to BKZ Q4W/Q8W

- Date of last BKZ 320mg Q8W dose in the OLE2 Period – date of first BKZ 320mg Q4W dose in the OLE2 Period + 56 days.

Note: If date of last bimekizumab dose in the OLE2 Period + 56 days extends to a date beyond the final visit date (including PEOT, but not including SFU2), then this calculation reverts to:

- Final visit date (including PEOT, but not including SFU2) – date of first BKZ 320mg Q4W dose in the OLE2 Period + 1.

Note: For subjects who die, if date of last bimekizumab dose in the OLE2 Period + 56 days extends to a date beyond the date of death, then this calculation reverts to:

- Date of death – date of first dose in the OLE2 Period + 1

- If the subject discontinued prior to the switch to Q8W then:

- Date of last BKZ 320mg Q4W dose in the OLE2 Period – date of first BKZ 320mg Q4W dose in the OLE2 Period + 28 days.

If date of last bimekizumab dose in the OLE2 Period + 28 days extends to a date beyond the final visit date (including PEOT, but not including SFU2), then this calculation reverts to:

- Final visit date (including PEOT, but not including SFU2) – date of first BKZ 320mg Q4W dose in the OLE2 Period + 1.

Note: For subjects who die prior to switch to Q8W, if date of last bimekizumab dose in the OLE2 Period + 28 days extends to a date beyond the date of death, then this calculation reverts to:

- Date of death – date of first dose in the OLE2 Period + 1.

## Time at risk (days)

- Attributed to BKZ Q4W/Q8W:
  - Use the time at risk algorithm specified for subjects who do not switch study treatments in Section 10.1.6.1.

## 10.2 Adverse events

An AE is any untoward medical occurrence in a subject or clinical investigation subject administered a pharmaceutical product that does not necessarily have a causal relationship with this treatment. An AE can therefore be any unfavorable and unintended sign (including an abnormal laboratory finding), symptom, or disease temporally associated with the use of a medicinal (investigational) product, whether or not related to the medicinal (investigational) product.

Adverse events will be coded according to the MedDRA. AEs will be allocated to the respective randomized treatment arm. For subjects who switch treatment at Week 16, Week 48 or (on or after Week 64), any adverse events that occur after initiation of the new treatment are attributable to the new treatment. If an adverse event occurs on the date of a treatment switch, the event is attributed to the original treatment. The only exception to this is if the AE fulfills any of the criteria specified below:

- Events that fulfill the anaphylaxis criteria for acute events
- Events that fulfill the hypersensitivity criteria
- Events with an HLT of “Administration site reactions NEC”
- Events with an HLT of “Injection site reactions”

For results disclosure on public registries (eg, ClinicalTrials.gov), treatment-emergent adverse events and treatment-emergent serious adverse events will be published.

### 10.2.1 Data considerations

TEAEs are defined as those AEs that have a start date on or following the first dose of study treatment through the final dose of study treatment + 140 days (covering the 20-week SFU period). If it is not possible (due to partial dates) to determine whether or not an AE is treatment-emergent then it will be assumed to be a TEAE.

The rules for imputing partial start or stop dates are outlined in Section 4.2.1.7.

If the intensity of an adverse event is unknown, it is considered as severe. If the relationship to study drug is missing, it is considered as related.

AEs will be presented as “number of subjects (percentage of subjects) [number of events]”. In this style of output, “[number of events]” will include all cases of an AE including repeat occurrences in individual subjects, while “number of subjects” will count each subject only once.

Subject time at risk represents the time a subject is at risk for having an AE. The definitions for subject time at risk (in days) are outlined in Section 10.1. These definitions will be used for exposure-adjusted AE summaries.

Selected AE summaries will include the exposure adjusted incidence rate (EAIR) with associated 95% CI and the exposure adjusted event rate (EAER).

The EAIR is defined as the number of subjects (n) with a specific AE adjusted for the exposure and will be scaled to 100 patient-years:

$$EAIR = 100 \times n / \sum_{i=1}^N (T_{Exp(i)})$$

Where  $T_{Exp(i)}$  is the exposure time for the  $i^{th}$  subject and N is the number of subjects at risk.

If a subject has multiple events, the time of exposure is calculated to the first occurrence of the AE being considered. If a subject has no events, the total time at risk is used.

Exact Poisson 95% confidence intervals for incidence rates are calculated using the relationship between the Poisson and the Chi-square distribution (Ulm, 1990; Fay and Feuer, 1997):

$$LCL = \chi^2_{2n, \alpha/2} / 2$$

$$UCL = \chi^2_{2(n+1), 1-\alpha/2} / 2$$

where n is the number of subjects with a specific AE for the incidence rate of interest and is the basis for the number of the degrees of freedom for the chi-square quantile for the upper tail probability  $\chi^2$ .

The EAER will be the number of AEs including repeat occurrences in individual subjects divided by the total time at risk scaled to 100 patient-years and calculated using:

$$EAER = 100 \times N_{AE} / \sum_{i=1}^N (T_{Risk(i)})$$

where  $N_{AE}$  is the total number of AEs,  $T_{Risk(i)}$  is the time at risk for then  $i^{th}$  subject, and N is the total number of subjects at risk.

No confidence interval will be computed for EAER.

Selected summaries, as specified in Section 10.2.2, will include the risk difference between bimekizumab and secukinumab. The risk difference is calculated as:

$$RD = IP_{BKZ} - IP_{SEC}$$

where  $IP_{BKZ}$  is the incidence proportion for the bimekizumab-treated group and  $IP_{SEC}$  is the incidence proportion for the secukinumab group. Note that incidence proportion simply refers to the percentage of subjects within the specified treatment group that experienced a given adverse event.

The standard error for the risk difference is calculated as follows:

$$SE_{RD} = \sqrt{\left( IP_{BKZ} \times \left( \frac{1 - IP_{BKZ}}{n_{BKZ}} \right) \right) + \left( IP_{SEC} \times \left( \frac{1 - IP_{SEC}}{n_{SEC}} \right) \right)}$$

where  $n_{BKZ}$  is the number of subjects in the bimekizumab-treated group and  $n_{SEC}$  is the number of subjects in the secukinumab group.

The corresponding confidence interval for the risk difference is as follows:

$$CI_{RD} = RD \pm Z_{1-\alpha/2} \times (SE_{RD})$$

where  $Z_{1-\alpha/2}$  is the Z statistic for the corresponding level of alpha. For the risk difference confidence intervals calculated in this SAP, 1.96 will be used (corresponding to a two-sided alpha of 0.05 and 95% confidence interval).

Separate by-subject listings of all TEAEs for the OLE and the OLE2 treatment periods will be provided.

